13.2 Definitions

Evaluable for toxicity: All patients will be evaluable for toxicity from the time of their first treatment with atezolizumab, carboplatin and etoposide.

Evaluable for objective response: Only those patients who have measurable disease present at baseline, have received at least one cycle of therapy, and have had their disease re-evaluated will be considered evaluable for response. These patients will have their response classified according to the definitions stated below. (Note: Patients who exhibit objective disease progression prior to the end of cycle 1 will also be considered evaluable.)

Evaluable Non-Target Disease Response: Patients who have lesions present at baseline that are evaluable but do not meet the definitions of measurable disease, have received at least one cycle of therapy, and have had their disease re-evaluated will be considered evaluable for non-target disease. The response assessment is based on the presence, absence, or unequivocal progression of the lesions. SBRT-treated liver lesions should not be counted as target lesions for disease response.

13.3 Disease Parameters

Measurable disease: Measurable lesions are defined as those that can be accurately measured in at least one dimension (longest diameter to be recorded for non-nodal lesions and short axis for nodal lesions) as ≥ 20 mm by chest x-ray, as ≥ 10 mm with CT scan, or ≥ 10 mm with calipers by clinical exam. All tumor measurements must be recorded in millimeters (or decimal fractions of centimeters).

Note: Tumor lesions that are situated in a previously irradiated area might or might not be considered measurable. If the investigator thinks it appropriate to include them, the conditions under which such lesions should be considered must be defined in the protocol.

Malignant lymph nodes: To be considered pathologically enlarged and measurable, a lymph node must be ≥ 15 mm in short axis when assessed by CT scan (CT scan slice thickness

recommended to be no greater than 5 mm). At baseline and in follow-up, only the short axis will be measured and followed.

Non-measurable disease: All other lesions (or sites of disease), including small lesions (longest diameter <10 mm or pathological lymph nodes with ≥ 10 to <15 mm short axis), are considered non-measurable disease. Bone lesions, leptomeningeal disease, ascites, pleural/pericardial effusions, lymphangitis cutis/pulmonitis, inflammatory breast disease, and abdominal masses (not followed by CT or MRI), are considered as non-measurable.

Note: Cystic lesions that meet the criteria for radiographically defined simple cysts should not be considered as malignant lesions (neither measurable nor non-measurable). Cystic lesions thought to represent cystic metastases can be considered as measurable lesions if they meet the definition of measurability described above. However, if non-cystic lesions are present in the same patient, these are preferred for selection as target lesions.

Target lesions: All measurable lesions up to a maximum of 2 lesions per organ and 5 lesions in total, representative of all involved organs, should be identified as target lesions and recorded and measured at baseline. The liver lesions that undergo SBRT will be excluded from the target lesions. Target lesions should be selected on the basis of their size (lesions with the longest diameter), be representative of all involved organs, but in addition should be those that lend themselves to reproducible repeated measurements. It may be the case that, on occasion, the largest lesion does not lend itself to reproducible measurement in which circumstance the next largest lesion which can be measured reproducibly should be selected. A sum of the diameters (longest for non-nodal lesions, short axis for nodal lesions) for all target lesions will be calculated and reported as the baseline sum diameters. If lymph nodes are to be included in the sum, then only the short axis is added into the sum. The baseline sum diameters will be used as reference to further characterize any objective tumor regression in the measurable dimension of the disease.

Non-target lesions: All other lesions (or sites of disease) including any measurable lesions over and above the 5 target lesions should be identified as non-target lesions and should also be recorded at baseline. Measurements of these lesions are not required, but the presence, absence, or in rare cases unequivocal progression of each should be noted throughout follow-up.

13.4 Methods for Evaluation of Measurable Disease

All measurements should be taken and recorded in metric notation using a ruler or calipers. All baseline evaluations should be performed as closely as possible to the beginning of treatment and never more than 4 weeks before the beginning of the treatment.

The same method of assessment and the same technique should be used to characterize each identified and reported lesion at baseline and during follow-up. Imaging-based evaluation is preferred to evaluation by clinical examination.

Conventional CT and MRI: This guideline has defined measurability of lesions on CT scan based on the assumption that CT slice thickness is 5 mm or less. If CT scans have slice thickness

**Columbia University Irving Medical Center
Herbert Irving Comprehensive Cancer Center
CUMC IRB – AAAT0174**

greater than 5 mm, the minimum size for a measurable lesion should be twice the slice thickness. MRI is also acceptable in certain situations (e.g., for body scans).

Use of MRI remains a complex issue. MRI has excellent contrast, spatial, and temporal resolution; however, there are many image acquisition variables involved in MRI, which greatly impact image quality, lesion conspicuity, and measurement. Furthermore, the availability of MRI is variable globally. As with CT, if an MRI is performed, the technical specifications of the scanning sequences used should be optimized for the evaluation of the type and site of disease. Furthermore, as with CT, the modality used at follow-up should be the same as was used at baseline and the lesions should be measured/assessed on the same pulse sequence. It is beyond the scope of the RECIST guidelines to prescribe specific MRI pulse sequence parameters for all scanners, body parts, and diseases. Ideally, the same type of scanner should be used and the image acquisition protocol should be followed as closely as possible to prior scans. Body scans should be performed with breath-hold scanning techniques, if possible.

PET-CT: At present, the low dose or attenuation correction CT portion of a combined PET-CT is not always of optimal diagnostic CT quality for use with RECIST measurements. However, if the CT performed as part of a PET-CT is of identical diagnostic quality to a diagnostic CT (with IV and oral contrast), then the CT portion of the PET-CT can be used for RECIST measurements and can be used interchangeably with conventional CT in accurately measuring cancer lesions over time. Note, however, that the PET portion of the CT introduces additional data which may bias an investigator if it is not routinely or serially performed.

Ultrasound: Ultrasound is not useful in assessment of lesion size and should not be used as a method of measurement. Ultrasound examinations cannot be reproduced in their entirety for independent review at a later date and, because they are operator dependent, it cannot be guaranteed that the same technique and measurements will be taken from one assessment to the next. If new lesions are identified by ultrasound in the course of the study, confirmation by CT or MRI is advised. If there is concern about radiation exposure at CT, MRI may be used instead of CT in selected instances.

Endoscopy/Laparoscopy: The utilization of these techniques for objective tumor evaluation is not advised. However, such techniques may be useful to confirm complete pathological response when biopsies are obtained or to determine relapse in trials where recurrence following complete response (CR) or surgical resection is an endpoint.

Cytology/Histology: These techniques can be used to differentiate between partial responses (PR) and complete responses (CR) in rare cases (e.g., residual lesions in tumor types, such as germ cell tumors, where known residual benign tumors can remain).

The cytological confirmation of the neoplastic origin of any effusion that appears or worsens during treatment when the measurable tumor has met criteria for response or stable disease is mandatory to differentiate between response or stable disease (an effusion may be a side effect of the treatment) and progressive disease.

FDG-PET: While FDG-PET response assessments need additional study, it is sometimes reasonable to incorporate the use of FDG-PET scanning to complement CT scanning in assessment of progression (particularly possible 'new' disease). New lesions on the basis of FDG-PET imaging can be identified according to the following algorithm:

- Negative FDG-PET at baseline, with a positive FDG-PET at follow-up is a sign of PD based on a new lesion.
- No FDG-PET at baseline and a positive FDG-PET at follow-up: If the positive FDG-PET at follow-up corresponds to a new site of disease confirmed by CT, this is PD. If the positive FDG-PET at follow-up is not confirmed as a new site of disease on CT, additional follow-up CT scans are needed to determine if there is truly progression occurring at that site (if so, the date of PD will be the date of the initial abnormal FDG-PET scan). If the positive FDG-PET at follow-up corresponds to a pre-existing site of disease on CT that is not progressing on the basis of the anatomic images, this is not PD.
- FDG-PET may be used to upgrade a response to a CR in a manner similar to a biopsy in cases where a residual radiographic abnormality is thought to represent fibrosis or scarring. The use of FDG-PET in this circumstance should be prospectively described in the protocol and supported by disease-specific medical literature for the indication. However, it must be acknowledged that both approaches may lead to false positive CR due to limitations of FDG-PET and biopsy resolution/sensitivity.

Note: A 'positive' FDG-PET scan lesion means one which is FDG avid with an uptake greater than twice that of the surrounding tissue on the attenuation corrected image.

13.5 Response Criteria

13.5.1 Evaluation of Target Lesions

Complete Response (CR): Disappearance of all target lesions. Any pathological lymph nodes (whether target or non-target) must have reduction in short axis to <10 mm.

Partial Response (PR): At least a 30% decrease in the sum of the diameters of target lesions, taking as reference the baseline sum diameters.

Progressive Disease (PD): At least a 20% increase in the sum of the diameters of target lesions, taking as reference the smallest sum on study (this includes the baseline sum if that is the smallest on study). In addition to the relative increase of 20%, the sum must also demonstrate an absolute increase of at least 5 mm. (Note: the appearance of one or more new lesions is also considered progression).

Stable Disease (SD): Neither sufficient shrinkage to qualify for PR nor sufficient increase to qualify for PD, taking as reference the smallest sum diameters while on study.

13.5.2 Evaluation of Non-Target Lesions

Complete Response (CR): Disappearance of all non-target lesions. All lymph nodes must be non-pathological in size (<10 mm short axis).

Non-CR/Non-PD: Persistence of one or more non-target lesion(s).

Progressive Disease (PD): Appearance of one or more new lesions and/or unequivocal progression of existing non-target lesions. Unequivocal progression should not normally trump target lesion status. It must be representative of overall disease status change, not a single lesion increase. Although a clear progression of “non-target” lesions only is exceptional, the opinion of the treating physician should prevail in such circumstances, and the progression status should be confirmed at a later time by the review panel (or Principal Investigator).

13.5.3 Evaluation of Disease Control Relative to the Radiation Field

In-field local control will be assessed in patients with at least 6 months of follow-up imaging post-SBRT. Follow-up images will be compared (by using image fusion software) with the SBRT treatment plan to evaluate local control (LC).

In-field local progression: Defined as new or progression lesions that develop within or at the margin of the radiation planning target volume (PTV)

Out-of-field progression: Defined as the development of lesions outside the PTV as assessed by RECIST v1.1. criteria.

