5.2 Intervention

All patients must undergo a mandatory biopsy of a liver lesion prior to chemotherapy initiation. Cycle 1 of chemoimmunotherapy will be administered as per standard of care, with radiation planning to be done subsequently in anticipation of liver-directed SBRT (3 doses of 10 Gy administered on alternating days to up to three liver lesions, measuring no greater than 5 cm each) to be given within +/-3 days of cycle 2.

Subjects will continue to receive study treatment (four 21-day cycles of induction chemoimmunotherapy followed by maintenance atezolizumab every 3 weeks) until disease progression or intolerance of treatment. During the maintenance phase, prophylactic cranial irradiation is permitted; consolidative thoracic radiation may be considered if deemed clinically appropriate by the treating investigator in discussion with the principal investigator.

If clinically feasible, it is recommended that the patient undergo a tumor biopsy sample collection at the time of radiographic disease progression. These data will be used to explore whether radiographic findings are consistent with the presence of a tumor. Additionally, these data will be analyzed to evaluate the association between changes in tumor tissue and clinical outcome and to further understand the potential mechanisms of progression and resistance to study treatment. This exploratory biomarker evaluation will not be used for any treatment-related decisions.

Patients will undergo tumor assessments prior to radiation administration and every 6 weeks (\pm 7 days) for the first 12 months following Cycle 1, Day 1, regardless of treatment dose delays. After 12 months, tumor assessments will be required every 9 weeks (\pm 7 days). Patients will undergo tumor assessments until radiographic disease progression per RECIST v1.1, withdrawal of consent, study termination by the principal investigator, or death, whichever occurs first.

Patients who continue treatment beyond radiographic disease progression per RECIST v1.1 will continue to undergo tumor assessments every 6 weeks (\pm 7 days), or sooner if symptomatic deterioration occurs. For these patients, tumor assessments should continue every 6 weeks (\pm 7 days), regardless of time in the study, until study treatment is discontinued.

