Patients who discontinue treatment for reasons other than radiographic disease progression (e.g., toxicity) will continue scheduled tumor assessments at the same frequency as would have been followed if the patient had remained on study treatment (i.e., every 6 weeks [\pm 7 days] for the first 12 months following Cycle 1, Day 1 and then every 9 weeks [\pm 7 days] thereafter, regardless of treatment dose delays) until radiographic disease progression per RECIST v1.1, withdrawal of consent, study termination by the principal investigator, or death, whichever occurs first, regardless of whether patients start a new anti-cancer therapy.

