6.5.2 Treatment Beyond Radiographic Progression

To better accommodate standard clinical practice which is guided by the fact that these patients have, in general, limited treatment options and such options also have limited efficacy and significant toxicity, patients may be considered for treatment beyond radiographic progression per RECIST v1.1 at the discretion of the investigator and after appropriate discussion with the patient and obtaining informed consent, only if all of the following criteria are met:

- Evidence of clinical benefit as assessed by the investigator
- Absence of symptoms and signs (including worsening of laboratory values [e.g., new or worsening hypercalcemia]) indicating unequivocal progression of disease
- No decline in ECOG performance status that can be attributed to disease progression
- Absence of tumor progression at critical anatomical sites (e.g., leptomeningeal disease) that cannot be managed by protocol-permitted medical interventions

- Patients must provide written consent to acknowledge deferring alternative treatment options in favor of continuing study treatment at the time of initial progression.

Patients who continue treatment beyond radiographic disease progression per RECIST v1.1 should be closely monitored clinically and a follow-up scan should be performed in 6 weeks, or sooner if symptomatic deterioration occurs. Treatment should be discontinued if clinical deterioration due to disease progression occurs at any time or if persistent disease growth is confirmed in a follow-up scan. In addition, patients should be discontinued for unacceptable toxicity or for any other signs or symptoms of deterioration attributed to disease progression as determined by the investigator after an integrated assessment of radiographic data and clinical status.

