- In-field local control will be defined as the absence of disease progression within the planning target volume (PTV) as per RECIST v1.1 on CT at 6 months following radiation treatment
- Out of field disease progression will be defined as the development of lesions outside the PTV as assessed by RECIST v1.1 criteria at 6 months following radiation treatment

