15.2 Analytical Plan

Descriptive statistics will be used to describe all the study endpoints. Mean (standard deviation) and/or median (interquartile range) will be used to summarize the continuous variables. Frequencies and percentages will be used to describe categorical variables.

The primary efficacy analysis will be based on the treated, response-evaluable . All patients who meet eligibility criteria, receive at least one dose of the study drug, and have evaluable 6-month outcomes will be included in the analysis of the primary and secondary endpoints, even if there are subsequent protocol deviations. Patients who withdraw from the study before on-treatment study effects can be assessed will be replaced

Analysis of Primary Endpoints

The 6-month PFS rate and its exact two-sided 95% confidence interval (CI) will be calculated. The primary analysis will be conducted after patients have been on treatment for 6 months. As secondary analysis, we will also evaluate the 6-month PFS as a time-to-event outcome using a non-parametric (Kaplan-Meier) or parametric Weibull model, based on the distribution of the survival function.

Analysis of Secondary Endpoints

The overall survival and progression free survival probabilities will be estimated using Kaplan-Meier method. The median survival and the corresponding 95% CI will also be provided.

**Columbia University Irving Medical Center
Herbert Irving Comprehensive Cancer Center
CUMC IRB – AAAT0174**

The estimates of the overall response rate (ORR), disease control rate (DCR), best overall response (BOR), duration of response, rate of in-field local control and out of field disease progression will be provided with the corresponding 95% CIs.

153 Size/Accrual Rate

The total sample of 18 patients is expected to be accrued over the course of two years (approximately 1 patient/month).

154 Stratification Factors

No stratification factors are applicable to this study.

155 Continuous Monitoring for Toxicity

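### In-field local control is rated only in patients with six months of post-SBRT imaging, so the outcome helps decide who is counted and early in-field failures can drop out

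*Combined protocol and SAP*

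**What the plan says.** The rate of in-field local control is a secondary objective (Section 2), and better local control is part of the stated hypothesis (Sections 1 and 3). Three passages govern the estimate:

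- Section 13.5.3 sets the denominator: "In-field local control will be assessed in patients with at least 6 months of follow-up imaging post-SBRT". It defines in-field progression as new or progressing lesions inside the PTV or at its margin.
- Section 15.1 defines control as no progression within the PTV "as per RECIST v1.1 on CT at 6 months following radiation treatment". It has no rule for a patient who fails, dies or stops imaging earlier.
- Section 15.2 says that patients who are eligible, treated and "have evaluable 6-month outcomes will be included in the analysis of the primary and secondary endpoints". It plans a rate with a 95% CI and no time-to-event estimate for this endpoint.

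Imaging is governed elsewhere. Section 5.2 states: "Patients will undergo tumor assessments until radiographic disease progression per RECIST v1.1", with withdrawal, study termination and death as the other end points; footnote 11 of the Section 12 calendar agrees. Patients who stop treatment without progression are still scanned, "until radiographic disease progression per RECIST v1.1, withdrawal of consent, study termination by the principal investigator, or death, whichever occurs first". Patients treated beyond progression are scanned every 6 weeks, "regardless of time in the study, until study treatment is discontinued". Under Section 6.5.2 that treatment should itself stop "if persistent disease growth is confirmed in a follow-up scan".

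**The concern.** Because patients who stop treatment for other reasons continue to be scanned, loss of imaging is tied mainly to progression or death. Requiring six months of imaging therefore selects the denominator by outcome.

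Take a new lesion at the PTV margin at week 12. It is in-field progression under Section 13.5.3 and progressive disease under Section 13.5.1. If the patient is not treated beyond progression, scheduled scans end, the six-month condition is never met, and a documented local failure leaves the failure rate.

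Local control is the most direct measure of what SBRT does to the lesions it treats. As written, its rate would come from a small selected group, and the plan does not ask for the numbers a reader would need to judge the selection.

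**Working it through.** **Plan's own figures.** The documents give no planned size, rate or precision for in-field control. The primary design in Section 15.1 reproduces: at least 6 of 16, null 20%, alternative 45%, gives exact one-sided alpha 0.082 and power 0.802; 16/0.9 = 17.8, so 18 accrued.

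**Inputs.** 6-month PFS (PFS6) of 20% or 45% (15.1). Median PFS 4.3 months with liver metastases on atezolizumab (Section 3). SBRT at cycle 2 day 1, taken as day 21 (11.2). One month = 30.44 days, so six months post-SBRT is 21 + 182.6 = day 204, or 6.70 months from treatment start.

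**Progression-free at six months post-SBRT.** Assume a Weibull curve through PFS6: S(t) = PFS6^[(t/6)^k]. One bound is k = 1 (exponential). The other comes from the 4.3-month median with PFS6 of 20%: k = ln(ln 5/ln 2)/ln(6/4.3) = 2.53.

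**Able to reach the qualifying scan.** A patient whose progression is first seen at the qualifying scan still has that scan, so the relevant time is the scan before it. The documents give two scan grids. Every 6 weeks from cycle 1 day 1 (5.2), the qualifying scan is week 30 and the one before is week 24 (5.52 months). Anchored at cycle 4 day 1 (13.1 and the calendar), these are week 33 and week 27 (6.21 months).

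| Time point | PFS6 20%: S (k = 1 / 2.53) | of 18 | PFS6 45%: S (k = 1 / 2.53) | of 18 |
|---|---|---|---|---|
| 6.70 months | 0.166 / 0.119 | 3.0 / 2.1 | 0.410 / 0.348 | 7.4 / 6.3 |
| Week 24 (week-30 scan) | 0.228 / 0.272 | 4.1 / 4.9 | 0.480 / 0.524 | 8.6 / 9.4 |
| Week 27 (week-33 scan) | 0.189 / 0.173 | 3.4 / 3.1 | 0.438 / 0.419 | 7.9 / 7.5 |

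Any patients imaged beyond progression add to these counts.

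**Precision.** With no failures among n patients, the exact 95% lower limit is 0.025^(1/n): 29% for 3/3, 40% for 4/4, 63% for 8/8, 66% for 9/9.

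**Bias.** Let C be true control at six months, with exponential in-field failure from SBRT. On the week-30 grid, control at week 24 (147 days after SBRT) is S24 = C^(147/183). Let r be the share of in-field failures seen by week 24 that are still imaged, divided by the same share among controlled patients. Then

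reported control = C / [S24 + r(1 − S24)].

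| Assumed C | S24 | r = 0 | r = 0.5 | r = 1 | r = 2 |
|---|---|---|---|---|---|
| 0.80 | 0.836 | 0.957 | 0.872 | 0.800 | 0.687 |
| 0.92 | 0.935 | 0.984 | 0.951 | 0.920 | 0.864 |

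Neither C nor r is in the documents. The 0.92 is 0.5^(6/51), from the 51-month median local control quoted in Section 3. That figure comes from a lesion-level series of mixed histologies and is used only to show a range.

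**Simulation check.** 400,000 patients per case, week-30 grid, C = 0.80 (true control at the week-30 scan 0.80^(189/183) = 0.794), in-field failure independent of other progression, deaths not separated, so the proposed estimate was checked as Kaplan-Meier.

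- If every in-field failure ends imaging, the plan's rule gives 0.95 and the proposed estimate 0.79. Of 2.0–3.2 in-field failures seen per 18 patients, the rule drops 1.8–2.7.
- If none ends imaging, both give 0.79–0.80.

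**The case against.** The strongest reply is that Section 15.2 can be read more kindly. For PFS6, a patient who progresses at month 3 has a known six-month outcome, and an in-field progressor at month 3 could be treated the same way. But Section 13.5.3 is the specific rule for this endpoint and sets its condition on duration of imaging. At best the sections disagree and the denominator is open to choice after the data are seen.

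The route to loss is also narrower than it first appears. Irradiated lesions are excluded from the target lesions (13.3), and growth of a single non-target lesion is not normally progression (13.5.2), so isolated regrowth may not end imaging. Some patients are scanned beyond progression. This stands: r = 0 is an extreme, and the direction of bias is not fixed. It is upward only if in-field failures are less likely than controlled patients to remain imaged.

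The week-30 count is fragile. If SBRT starts 3 days late and six months runs from the third alternate-day fraction, the mark is day 21 + 3 + 4 + 182.6, about day 211, after the week-30 scan on day 210. If week 36 then qualifies, about 2–3 or 6–7 of 18 remain. That makes the denominator smaller and does not remove the selection.

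Finally, a single sentence counting earlier in-field failures might seem enough. Alone it would overcorrect: if controlled patients whose imaging ended early stay excluded, simulation gave 0.60–0.73 for a true 0.79.

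**Conclusion.** The concern holds. The written rule makes inclusion depend on outcome, and an in-field failure that ends imaging before six months is not counted. The qualifying group is about 2–5 of 18 at PFS6 20%, or 6–9 of 18 at 45%, before adding any patients imaged beyond progression. For an assumed true control of 0.80, the reported figure could lie anywhere from about 0.69 to 0.96 as r runs from 2 to 0. The counts rest on the Weibull range; the bias figures rest on exponential in-field failure and assumed values of C and r.

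The consequence is limited: the endpoint is descriptive, no decision rule uses it, and the PFS6 test is untouched. It should still be corrected before analysis, because the rate as planned could not be interpreted.

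**What to change.** For this endpoint, remove the six-month imaging condition from Section 13.5.3 and state in Sections 15.1 and 15.2 that a six-month CT is not required. Then specify:

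1. Include every patient who received at least one SBRT fraction.
2. Count in-field progression as a failure whenever it is seen, up to and including the first scheduled scan at or after six months post-SBRT.
3. Report cumulative incidence at that point with a 95% CI, with death as a competing event and other patients censored at their last evaluable scan. Use scans after out-of-field progression where they exist.
4. Report how many patients failed in-field, died or were censored before six months.

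The cut-off needs one scan grid, so Sections 5.2 and 13.1 must be reconciled. So must the SBRT timing in Section 11.2 and calendar footnote 8, although that moves the six-month mark only by days.

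The cost is wording in three sections and a competing-risk estimate from scans already scheduled. The figure is less simple and may be less favourable. Because no imaging is added, many patients may be censored at out-of-field progression, and that censoring may not be independent. The report should say so.
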